### **9.2 Statistical and Analytical Plans**

#### **a. General Considerations**

All analysis would be conducted with the assistance or validation of a biostatistician. SPSS or Strata would be used to conduct the analysis. All categorical data would be analysed using the Fisher Exact Test. All continuous variables would be analysed using the Mann-Whitney U test. The level of statistical significance would be set as  $p < 0.05$ .

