## **1.2 Rationale and Justification for the Study**

We would be conducting a single-centre RCT simultaneously comparing the conventional open Milligan-Morgan haemorrhoidectomy (COH) and the laser haemorrhoidoplasty procedure (LAH) for the treatment of symptomatic grade II-IV haemorrhoids. Primary outcomes will be post-operative pain while secondary outcomes include post-operative bleeding, readmission and/or reoperations, haemorrhoid-related quality of life (QoL) results and recurrence of symptoms up to a year post procedure.

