### **2.3 Secondary Objectives**

- Operative duration
- Incidence of post-operative bleeding
- Incidence of readmission to haemorrhoidectomy/haemorrhoidoplasty related symptoms/condition (pain/pelvic symptoms/bleeding)
- Procedure-related complications (thrombosis, fistulation, incontinence, stenosis)
- Incidence and timing of recurrence of haemorrhoid-related symptoms
- Haemorrhoid-specific QoL questionnaire (Haemorrhoid Severity Score)

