## 4.3 Study Visits and Procedures

### 4.3.1 Screening Visits and Procedures

Patients will be seen in the clinic or in the wards for symptomatic haemorrhoids. All these patients would be approached and be introduced to this study but not recruited yet.

Figure 2 illustrates the visits commitment throughout the study process. After the completion of surgery, patients typically would already have a follow up appointment at 4-6 weeks after the procedure. The clinician will assess the patients progress and examining them for any complications. If their recovery is smooth, most of these patients would be discharged from follow up. During the same setting, the research administrators would collect back the peri-operative package from the patient.

Research administrators would then conduct a phone interview with the patients at 3-month and 1-year after surgery to perform the QoL survey and also looking out for late-onset complications and recurrence of symptoms. If present, they will be offered to have an appointment booked with their primary surgeon. Patients would be informed of the allocation at the clinic review at 4-6 weeks. As none of the visits are outside of normal practice, no remuneration is required.

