### **4.4.2 Discontinuation Visit and Procedures**

Upon voluntary withdrawal, participants would resume regular follow up as per clinical requirement. These patients would not receive a phone interview at 3-months and a year after the procedure. These patients would also be given an open date in the clinic to allow them a year in duration to return to the clinic for evaluation if there are recurrence of symptoms or development of a previously unrecognised complication from either of the procedures.

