## **9 SAMPLE SIZE AND STATISTICAL METHODS**

### **9.1 Determination of Sample Size**

Based on previous studies, as well as unpublished results from surgeons who have performed LAH around the South East Asian region, we are expecting 50% of the patients in the COH arm to have a VAS score of more than 7.5. We expect to see 25% patients in the LAH arm having a VAS score of more than 7.5.

With a power of 80%, chance of type 1 error (alpha) less than 5% and accounting for 10% of loss to follow up rate, the sample size required for the study to be adequate powered is having 64 patients in each arm (N=128).

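### Protocol section 9.2 assigns the Mann-Whitney test to every continuous variable, a poor fit for the censored timing of recurrence listed in section 2.3 (minor)

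*Protocol*

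**What the plan says.** Section 9.2(a) has one test for each type of data. Categorical data go to Fisher's exact test. For the rest: "All continuous variables would be analysed using the Mann-Whitney U test". No time-to-event method appears.

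Section 2.3 lists as a secondary objective "Incidence and timing of recurrence of haemorrhoid-related symptoms". Section 1.2 sets the horizon: "recurrence of symptoms up to a year post procedure". After the 4-6 week clinic review, section 4.3.1 has research administrators "conduct a phone interview with the patients at 3-month and 1-year after surgery".

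Some patients will be observed for less than a year. The sample size in section 9.1 was set "accounting for 10% of loss to follow up rate". Section 4.4.2 says of patients who withdraw: "These patients would not receive a phone interview at 3-months and a year after the procedure". The same section returns them to ordinary clinical follow-up, and they are also "given an open date in the clinic to allow them a year in duration to return to the clinic".

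**The concern.** Incidence of recurrence is a yes/no outcome and Fisher covers it. Timing is a duration, so its natural place under section 9.2 is the Mann-Whitney rule. But a patient with no recurrence has no recurrence time, only the knowledge that none was seen up to the last contact. Mann-Whitney needs a value or a rank for every patient it includes, and the protocol gives no rule for these patients. The answer on timing then depends on a coding that could be chosen after the data are seen.

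This is more than detail left to a statistical analysis plan. Section 9.2 is worded to cover all continuous variables, so a later plan that used a log-rank test for timing would depart from the protocol's text. Section 1.2.1 partly justifies the trial by the lack of randomised evidence on longer-term outcomes, and recurrence to one year is one of these.

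**Working it through.** **The plan's own figure.** Section 9.1 gives no figure for recurrence; its 64 per arm is for the proportion with VAS above 7.5 (50% v 25%, 80% power, 5% alpha, taken as two-sided). With the pooled formula:

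n = [1.960·√(2·0.375·0.625) + 0.842·√(0.50·0.50 + 0.25·0.75)]² / 0.25² = (1.342 + 0.557)² / 0.0625 ≈ 57.7, so 58 per arm.

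58 × 1.10 = 63.8, so 64, as stated (58 / 0.90 = 64.4 would give 65). The figure reproduces, and recurrence plays no part in it.

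**Inputs for the check.** From the protocol: 64 per arm, one-year horizon, 10% loss, 5% significance level. Assumed: one-year recurrence rates, loss by arm, use of the 10% as one-year loss, and loss independent of recurrence.

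**Ways to apply the rule to timing**

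1. *Recurrers only.* At 10 v 30%, about 6.4 + 19.2 ≈ 26 of 128 patients would enter the test, fewer after loss. They are selected by an event after randomisation, and how many recur does not enter the comparison.
2. *Last-contact time for everyone.* A patient lost at four months ranks like one who recurred at four months. The share with a time below one year is 1 − (1 − recurrence)(1 − loss). With equal recurrence of 20% and loss of 5 v 15%, this is 1 − 0.80·0.95 = 24% v 1 − 0.80·0.85 = 32%: an apparent difference made by loss alone.
3. *All non-recurrers tied after every recurrence.* This uses all patients and reflects both how many recur and when, but treats lost patients as never recurring.
4. *Recurrence tabulated by contact, with Fisher.* This treats timing as categorical and ignores the order of the contacts.

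**Simulation.** Exponential recurrence times, 64 per arm, two-sided 5%. The first figure in each cell is from 5,000 trials per scenario with loss uniform over the year; the second is from 2,000 trials with exponential loss. Rejection rates in %:

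| Recurrence; loss | Recurrers only | Last contact | Tied last | Log-rank |
|---|---|---|---|---|
| 10 v 30; 10 v 10 | 4.4 / 5.1 | 62.6 / 62.0 | 80.9 / 80.3 | 81.5 / 81.1 |
| 10 v 30; none | – / 4.3 | 82.4 / 81.7 | 82.4 / 81.7 | 82.8 / 82.0 |
| 20 v 20; 10 v 10 | – / 5.3 | 4.6 / 4.8 | – / 5.1 | – / 5.0 |
| 20 v 20; 5 v 15 | – / 5.3 | 15.5 / 16.8 | 5.5 / 4.2 | 5.3 / 4.0 |

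The recurrers-only figures at 10 v 30% are not a failed test of incidence; that test asks a different question.

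At 10 v 30% with unequal loss (exponential loss model), last-contact power is 92% when the 30% arm has the higher loss (15 v 5%) and 22% when it has the lower. Log-rank gives 80 to 81% in both; tied last gives 76% and 85%, so it is not wholly neutral.

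If recurrence is dated only by the contact at which it is found (5 weeks, 3 months, 12 months; 10 v 30%, 10% loss per arm), last-contact power is 13%, tied last 78%, log-rank 79%, and Fisher on the 2×4 table 67%. That Fisher test keeps its error rate: 4.1% and 5.1% at equal recurrence of 10% and 20% with loss of 5 v 15%.

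**The case against.** The strongest objection is that the protocol fixes nothing wrong. Coding of non-recurrers is commonly left to a statistical analysis plan, section 9.2(a) provides for a biostatistician, and no section calls timing of recurrence continuous. Tied-last Mann-Whitney obeys the rule and comes within about one point of log-rank in the first two rows of the table. Timing by contact with Fisher also obeys it. Much of this stands: a reader might infer that Mann-Whitney is invalid for this outcome, and the documents do not support that. What remains is that the rule covers all continuous variables and does not state the coding that would make it work.

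A reader might also take the 16 to 17% as the error rate that section 9.2 produces. It is not. It needs the last-contact coding, which the protocol does not prescribe, and unequal loss, which is assumed. With equal loss the rate is about 5%. Unequal loss is possible, since "Patients would be informed of the allocation at the clinic review at 4-6 weeks", before both phone interviews, but nothing in the protocol predicts it.

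Loss prompted by knowing the allocation might also depend on symptoms, and log-rank is then not safe either. With equal true recurrence of 10/20/30%, 5% random loss per arm, and 30% of would-be recurrers in one arm lost before recurrence (all assumed), log-rank rejects 7.8/10.9/14.6% and last-contact Mann-Whitney 4 to 5%. The ranking of methods therefore depends on the loss model.

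It would be too strong to say that withdrawn patients are no longer seen. Section 4.4.2 keeps them in ordinary clinical follow-up and adds the open clinic date; what they lose is the two scheduled interviews. Finally, the 10% loss belongs to a sample size for pain scored over ten days, so its use as one-year loss is an assumption.

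**Conclusion.** The concern holds as a poor fit between a stated blanket rule and one outcome. It is minor. Under the 10% loss used here, the last-contact reading costs about 19 points of power (62% against 81 to 82% at 10 v 30%), and it can produce false differences if loss differs between arms. The recurrers-only reading does not address the randomised comparison. The tied-last reading largely avoids the problem but is unstated. Without early loss and with onset dated, last contact and tied last coincide.

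The effect is confined to the timing half of one secondary objective. Recurrence is not in the hypothesis (section 2.1). The pain analysis, the 64 per arm and Fisher for incidence stand. Nor would log-rank transform the recurrence comparison: over the three effect scenarios run (5 v 15%, 5 v 25%, 10 v 30%), it gains about 4 to 8 points over Fisher on incidence at 10% loss, and 5 to 12 points with no loss. All of these sizes rest on assumed recurrence rates and on loss unrelated to recurrence.

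**What to change.** In section 9.2(a), exempt timing of recurrence from the Mann-Whitney rule and add:

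> Time to recurrence will be shown by Kaplan-Meier curves by arm and compared by the log-rank test in all randomised patients, censoring those without recurrence at last contact.

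Keep Fisher for incidence, and leave the other continuous secondary outcomes under Mann-Whitney. If Mann-Whitney is preferred for timing as well, state that all patients without observed recurrence are ranked tied after every recurrence.

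The cost is small: one sentence, with no extra patients or visits. The date of last contact and, where the patient can give it, of symptom onset must be recorded if the forms do not already hold them; the questionnaire package is attached separately and could not be checked. The downside is that log-rank assumes loss unrelated to recurrence, so loss by arm should be reported beside the result.

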## **4 STUDY DESIGN**

This is a single-center, double-blind randomized controlled trial to be conducted in Sengkang General Hospital.

All patients presenting to the clinic or admitted for symptomatic haemorrhoids would be assessed for recruitment.

Figure 1 shows the enrolment process of the study population in the trial. Patients will be seen in the

clinic or in the wards for symptomatic haemorrhoids. All these patients would be approached and be introduced to this study but not recruited yet.

Patients older than 40 years-old with no recent colonoscopy (within 5 years) would need to have a colonoscopic evaluation of the colon after the index admission/clinic visit.

Those younger than 40 would be advised to have a rigid sigmoidoscopy on the day of the operation during the examination under anaesthesia. Only after agreement to the above, the patient would be recruited into the study. They would then be educated on the peri-operative questionnaire separately by a research administrator after recruitment into the trial.

The peri-operative package is split into pre- and post-operative components and will include basic demographics, baseline haemorrhoid-specific QoL questionnaires, VAS scales for POD0-10 and details of the intraoperative procedure and intraoperative description of the haemorrhoids.

Patients who fit the inclusion and exclusion criteria would be recruited into the study. We will perform a 1:1, block-of-4 randomization using a computer-generated programme performed by an independent research administrator who is not part of the surgical team.

They will be allocated only after they are examined under anaesthesia. Allocation is provided in a concealed opaque envelope that is provided by the research administrator on the day of the operation. Thus, the patient is blinded to the procedure. There will also be no cross-over from one study arm to another.

Potential Difficulties and Alternative Approaches to achieve the aims:

Difficulty of recruitment of patients into the trial may be potentially present especially for a procedure that is new in Singapore. Patient counselling and explanation of the procedure would be important and offering a short video clip of the procedure may be helpful. The procedurists/co-investigators of the study team would also be trained by a regional practitioner of the technique before the initiation of the trial to ensure proficiency for reassurance.

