#### **4.1 Randomisation and Blinding**

Patients who fit the inclusion and exclusion criteria would be recruited into the study. We will perform a 1:1, block-of-4 randomisation using a computer-generated programme performed by an independent research administrator who is not part of the surgical team.

They will be allocated only after they are examined under anaesthesia. Allocation is provided in a concealed opaque enveloped that is provided by the research administrator on the day of the operation. Thus, the patient is blinded to the procedure. There will also be no cross-over from one study arm to another.

An independent research administrator, not part of the randomisation process, will also contact the patient 3 months and 1 year after the procedure as mentioned above.

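### Follow-up haemorrhoid-specific quality of life is fixed to an unadjusted Mann-Whitney test although its own baseline is collected: valid, but less efficient than it could be at no data cost

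*Protocol*

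**What the plan says.** Section 9.2a assigns one test to each type of variable: "All categorical data would be analysed using the Fisher Exact Test" and "All continuous variables would be analysed using the Mann-Whitney U test". It adds "The level of statistical significance would be set as" p < 0.05. It mentions no covariate or baseline term. Because both sentences cover all variables of their type, the choice is fixed in the protocol. An adjusted main analysis in a later analysis plan would depart from it.

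Section 2.3 lists the haemorrhoid-specific quality-of-life questionnaire, named there as the Haemorrhoid Severity Score, as a secondary outcome. Section 2.1 includes better quality-of-life scores at 1 and 3 months in the hypothesis. Section 4 puts "baseline haemorrhoid-specific QoL questionnaires" in the peri-operative package, along with daily pain scores from the day of surgery to day 10 and a description of the haemorrhoids made in theatre. No pre-operative pain score is listed. Sections 4.3.1 and 6.5 describe the quality-of-life survey by telephone at 3 months and 1 year.

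On allocation, section 4.1 says "We will perform a 1:1, block-of-4 randomisation". It names no stratification factor and places allocation after the examination under anaesthesia.

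**The concern.** A follow-up score on a symptom and quality-of-life instrument usually depends in part on where the patient started. When the same instrument has been completed at baseline, conditioning on it removes that part of the between-patient variation. A two-sample Mann-Whitney test on the follow-up score leaves that variation in the noise.

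What is at stake is the power and precision of a comparison that the hypothesis names, in a trial with roughly 58 evaluable patients per arm. The unadjusted test also takes no account of any baseline difference that happens to arise in the trial actually run. Severity ranges from grade II to grade IV (section 1.2.4), so some such difference is plausible.

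**Working it through.** **1. Reproduce the plan's sample size.** Section 9.1 states "we are expecting 50% of the patients in the COH arm to have a VAS score of more than 7.5" and "We expect to see 25% patients in the LAH arm having a VAS score of more than 7.5". It continues "With a power of 80%, chance of type 1 error (alpha) less than 5% and accounting for 10% of loss to follow up rate" and arrives at 64 per arm. Sidedness is not given; two-sided is assumed.

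n = [1.960 × √(2 × 0.375 × 0.625) + 0.842 × √(0.5 × 0.5 + 0.25 × 0.75)]² / 0.25² = 57.7, rounded up to 58 per arm.

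With 10% loss: 58 × 1.1 = 63.8, so 64; or 58 / 0.9 = 64.4, so 65. The stated figure reproduces. It rests on an unadjusted comparison of two proportions and does not rely on covariate adjustment, so leaving adjustment out creates no arithmetic error. Conversely, 64 × 0.9 = 57.6, so about 58 evaluable per arm is used below. Applying that figure to the quality-of-life outcome is an assumption.

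**2. Gain from conditioning on baseline.** For a continuous outcome, ANCOVA multiplies the residual variance by (1 − r²), where r is the baseline to follow-up correlation. The protocol gives no r, so a range is shown. As a reference, take the standardised effect that an unadjusted comparison of means detects with 80% power at 58 per arm:

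d = (1.960 + 0.842) × √(2/58) = 0.52.

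Power after adjustment is Φ(2.802/√(1 − r²) − 1.960). The number per arm that would then give 80% power is 58 × (1 − r²), rounded up.

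| r (assumed) | 1 − r² | ANCOVA power | n per arm for 80% |
|---|---|---|---|
| 0 | 1.00 | 80.0% | 58 |
| 0.1 | 0.99 | 80.4% | 58 |
| 0.2 | 0.96 | 81.6% | 56 |
| 0.3 | 0.91 | 83.6% | 53 |
| 0.4 | 0.84 | 86.4% | 49 |
| 0.5 | 0.75 | 89.9% | 44 |

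**3. Check against the test actually planned.** This was a simulation with normal data, 58 per arm, d = 0.53 and 4,000 runs per setting. The Monte Carlo standard error near 80% is √(0.8 × 0.2/4000) = 0.6 points.

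| r (assumed) | Mann-Whitney | ANCOVA | Rank ANCOVA |
|---|---|---|---|
| 0.1 | 79.3% | 81.1% | 79.1% |
| 0.2 | 79.3% | 82.2% | 80.2% |
| 0.3 | 79.0% | 83.6% | 81.9% |
| 0.5 | 78.8% | 90.0% | 87.5% |

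Rank ANCOVA keeps the robustness that motivates a rank test. It gains nothing at r = 0.1, about 3 points at r = 0.3 and almost 9 points at r = 0.5.

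**4. Validity.** With no treatment effect, the Mann-Whitney test rejected in 4.3 to 5.2% of runs for r from 0 to 0.5. Both adjusted tests stayed between 4.6 and 5.2%.

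**5. Chance imbalance.** At 58 per arm the standardised baseline difference has standard deviation √(2/58) = 0.19. It exceeds 0.25 standard deviations with probability 18%, and 0.5 with probability 0.7%.

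**The case against.** The strongest reply is that nothing here is wrong. Unadjusted tests after randomisation hold their error rate, and that rate already allows for chance imbalance. Section 9.1 is unadjusted too, so the plan is consistent with itself. A rank test is a reasonable choice for a bounded and possibly skewed score. The gain depends on a correlation that the protocol does not supply. Even for quality of life it cannot be taken as large, because the baseline sits in the peri-operative package while the 3-month and 1-year surveys are by telephone. All of this stands. It limits the point to efficiency, but does not remove the case for using a baseline that is collected anyway.

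A reader might go further in several ways that the documents do not support:

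- **That every outcome, including primary pain, loses precision.** No baseline pain score is listed, and nothing in the protocol shows that the severity score or haemorrhoid grade predicts post-operative pain. The (1 − r²) factor applies to a continuous outcome. It does not carry over to the proportion with VAS above 7.5 on which the trial is sized.
- **That unstratified randomisation leaves the results biased.** It does not, as the simulated error rates show.
- **That haemorrhoid grade is a ready-made covariate.** The description is made in theatre. The protocol does not say that it is written down before the envelope is opened.
- **That effect sizes and intervals are ruled out.** Naming a test does not prevent their being reported, and such detail is often left to an analysis plan.
- **That Fisher's exact test should go too.** For rare complications it is a sensible choice.

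**Conclusion.** The point holds for one outcome. The protocol fixes an analysis of the follow-up Haemorrhoid Severity Score that cannot use the baseline already collected. This is an avoidable loss of efficiency in a valid analysis. It calls for an improvement and not the correction of an error.

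Its size is conditional: about 0 to 2 points of power at r = 0.1 to 0.2, about 4 at r = 0.3 and about 10 at r = 0.5 with ANCOVA, and somewhat less with rank ANCOVA. The figures assume 58 evaluable patients per arm, a two-sided 5% level, roughly normal scores and a linear relation to baseline. They also assume that the baseline questionnaire is the instrument used at follow-up, which sections 2.3 and 4 suggest but do not spell out. The 80% starting value is a reference only, since the trial was not sized on quality of life.

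For pain, adjustment for the baseline score is at most a supportive analysis of unknown gain.

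**What to change.** In section 9.2a, replace the blanket rule for continuous variables as it applies to quality of life:

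- Make the main comparison of the follow-up Haemorrhoid Severity Score at each time point an ANCOVA on the baseline score, or a rank or ordinal regression if the distribution calls for it.
- Report the adjusted difference with its 95% confidence interval.
- Keep the Mann-Whitney test as a sensitivity analysis.
- Keep Fisher's exact test for rare complications.

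Optionally, add a supportive analysis of pain adjusted for the baseline score, described as such. Use haemorrhoid grade as a covariate only if it is recorded before the envelope is opened.

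The cost is a change of wording and slightly more analysis work, with no new data. Using grade would also require its recording before allocation to be fixed in theatre procedure. The sample size does not change.
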